7.3. Unscheduled Visits

If, during the investigation, a subject requires an unscheduled visit to the clinical site, the following information will be collected, as appropriate:

- Chief complaint prompting the visit. If the reason is an adverse event, the applicable eCRF for the adverse event must be completed and subject record completed as appropriate.
- Date and time of the visit and all procedures completed at the unscheduled visit.
- Review of adverse event and concomitant medications.
- Documentation of any test article dispensed or collected from the subject, if applicable.
- Slit lamp findings (using the Slit Lamp Classification Scale).

If the Investigator withdraws a subject from the study, the final study visit case report forms must be completed indicating the reason(s) why the subject was withdrawn. The subject record must be completed documenting the date and primary reason for withdrawal and the study CRA notified.

Any ocular and non-ocular Adverse Events that are ongoing at the time of the study visit will be followed by the Investigator, within licensure, until they have resolved, returned to pre-treatment status, stabilized, or been satisfactorily explained. If further treatment i.e., beyond licensure is required, the subject will be referred to the appropriate health care provider.

The following information will be collected, if applicable, during an unscheduled visit.

Unscheduled Visit		
Step	Procedure	Details
U.1	Reason for unscheduled visit	Indicate if the only reason for the visit is that the subject requires additional test articles. If the reason is other than resupply of previously dispensed lenses, specify the reason for the visit.
U.2	Chief Complaints (if applicable)	Record the subject's chief complaints for reasons for the unscheduled visit.
U.3	Adverse Events and Concomitant Medications Review (if applicable)	Review any changes to the subject's medical history or concomitant medications from the previous study visit. Record any changes, and any adverse events.

Clinical Study Protocol
Johnson & Johnson Vision Care, Inc.

Unscheduled Visit			
Step	Procedure	Details	
U.4	Entrance VA (if applicable)	Record the entrance distance visual acuity (OD, OS) to the nearest letter with habitual correction or uncorrected.	
U.5	Monocular Subjective Best Sphere Over Refraction (if subject's chief complaint is blurry vision with study contact lens(es))	
Perform monocular subjective best sphere refraction over the study lenses with a phoropter.
 
 • Reduce minus (add plus) in 0.25 D steps if there is no decrease in visual acuity and no subjective vision reduction. • Increase minus in 0.25 D steps if it significantly improves distance vision. • Record the spherical power and the resultant distance visual acuity to the nearest letter (OD, OS). 	
U.6	Lens Power Modification (if applicable)	
Refer to the respective fitting guide to determine whether a lens power modification is needed.
 
For each power modification, select the new lens power as appropriate and repeat the steps beginning with right lens insertion.
 
A maximum of 2 lens modifications are allowed per eye. If, for either eye, the fit is not successful after 2 modifications, the subject will be discontinued (proceed to final evaluation).
	Appendix G
U.7	Subjective Sphero-cylindrical Refraction (if applicable)	Perform bare-eye subjective spherocylindrical refraction with a phoropter (adopt the maximum plus to maximum visual acuity (MPMVA) approach and use the duo-chrome test for binocular balancing) and record the best corrected distance visual acuity to the nearest letter (OD, OS).	

Clinical Study Protocol
Johnson & Johnson Vision Care, Inc.

Unscheduled Visit																				
Step	Procedure	Details																		
U.8	Distance logMAR VA with spherocylindrical prescription	
Measure distance ETDRS logMAR visual acuity at a 4 meter (m) distance with spherocylindrical prescription in a trial frame using the conditions and charts shown in the table below:
 
 
 Distance	4 m	4 m	
 
 Condition	HLHC	HLHC	
 
 Room illumination	686-788 lux	686-788 lux	
 
 Chart luminance	181-208 cd/m²	181-208 cd/m²	
 
 Eye	OD	OS	
 
 Charts (Numbers)	HC-3 (2114B)	HC-4 (2114C)	
 
 
Note: If logMAR VA measures more than 0.15 logMAR worse than at baseline, the measurement should be repeated. If the visual acuity reduction is confirmed, an adverse event will be filed. The subject will be followed until visual acuity is no more than 0.15 logMAR worse than baseline or is stabilized before being discontinued.
 
Note 2: per ISO 11980, a loss of two or more lines (0.20 logMAR) of best corrected visual acuity for greater than or equal to 2 weeks is considered a significant or serious adverse event depending on the duration.
	Distance	4 m	4 m	Condition	HLHC	HLHC	Room illumination	686-788 lux	686-788 lux	Chart luminance	181-208 cd/m ²	181-208 cd/m ²	Eye	OD	OS	Charts (Numbers)	HC-3 (2114B)	HC-4 (2114C)
Distance	4 m	4 m																		
Condition	HLHC	HLHC																		
Room illumination	686-788 lux	686-788 lux																		
Chart luminance	181-208 cd/m ²	181-208 cd/m ²																		
Eye	OD	OS																		
Charts (Numbers)	HC-3 (2114B)	HC-4 (2114C)																		
U.9	Slit Lamp Biomicroscopy (if applicable)	
Slit Lamp Classification Scale per ISO 11980 will be used to grade the findings. If the clearance of the fluorescein needs to be expedited, preservative-free rewetting drops or saline may be instilled.
 
Note: If any slit lamp finding is graded as 2 (except for subjects with Grade 2 baseline palpebral conjunctival observations) or worse, it may warrant classification of an adverse event, and shall be followed
																		

Clinical Study Protocol
Johnson & Johnson Vision Care, Inc.

Unscheduled Visit		
Step	Procedure	Details
		accordingly. A subject with significant slit lamp findings (e.g., Grade 3 corneal staining, Grade 2 corneal neovascularization, anterior segment inflammation, and corneal infiltrate, etc.) may not be dispensed study contact lenses at this time and an adverse event form must be completed. The subject must be followed until slit lamp findings are resolved and the investigator deems it's appropriate for the subject to continue with the study before contact lens dispensing. If the subject is discontinued from the study, the Final Evaluation must be completed.
U.10	Dispensing (if applicable)	If the subject requires additional lenses to complete the wear period and is eligible to do so, provide additional lenses per the dispensing instructions given in the detailed study procedures.
U.11	Exit Visual Acuity (if applicable)	Record the subject's exit distance visual acuity (OD, OS) to the nearest letter.

NOTE: If the only reason for the unscheduled visit is that the subject requires additional test articles, only the dispensing information needs to be recorded.

7.4. Laboratory Procedures

Not applicable.

8. SUBJECTS COMPLETION/WITHDRAWAL

8.1. Completion Criteria

Subjects are considered to have completed the study if they:

- provided informed consent.
- they are eligible.
- have not withdrawn/discontinued from the study for any reason described in section 8.2.
- completed all visits through the final visit (visit 5).
- If all visits were completed but an additional visit is considered necessary for subject care, follow the requirements for unscheduled visits in section 7.3.

Clinical Study Protocol

Johnson & Johnson Vision Care, Inc.

8.2. Withdrawal/Discontinuation from the Study

A subject will be withdrawn from the study for any of the following reasons:

- Subject withdrawal of consent.
- Subject not compliant to protocol (e.g., refusing any protocol specified procedure)
- Subject lost to follow-up.
- Subject no longer meets eligibility criteria (e.g. the subject becomes pregnant).
- Subject develops significant or serious adverse events necessitating discontinuation of study lens wear
- Subjects who have experienced a Corneal Infiltrative Event (CIE).
- Investigator's clinical judgment regarding the subject safety reasons (that it is in the best interest of the subject to stop treatment).
- Subject not compliant with study lens wear schedule
- Subject not successfully dispensed due to lack of efficacy and safety including poor vision, poor comfort or unacceptable fit.

For discontinued subjects, the Investigator will:

- Complete the current visit (scheduled or unscheduled).
- Complete the Final Evaluation, indicating the reason that the subject was discontinued from the study.
- Record the spherocylindrical refraction with best corrected distance visual acuity.
- Collect used test article(s) (worn or brought to the visit) from the subject and discard them, unless otherwise stated in section 7.2
- Collect all unused test article(s) from the subject.
- Make arrangements for subject care, if needed, due to their study participation

Additional subjects will not be enrolled if a subject discontinues from the study prematurely.

In cases where a subject is lost to follow-up, every possible effort must be made to contact the subject and determine the reason for discontinuation/withdrawal. The measures taken to follow up must be documented including two written attempts and a certified letter (or equivalent) as the final attempt.

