10. DEVIATIONS FROM THE PROTOCOL

Investigator will notify study sponsor upon identification of a protocol deviation. Protocol deviations must be reported to the sponsor within 24 hours after discovery of the protocol deviation. The Investigator will report deviations per IRB/IEC requirements. All deviations will be tracked, and corrective actions implemented as appropriate.

If it becomes necessary for the Investigator to implement a deviation in order to eliminate an immediate hazard to the trial subject, the Investigator may implement the deviation immediately without notification to the sponsor. Within 24 hours after the implemented deviation, the Investigator must notify and provide the rationale to the Sponsor and, as required, the IEC/IRB.

If the deviation potentially impacts the safety of patient or changes the technical integrity of the study, then it must be reported to IEC/IRB. This is a "Major Deviation". Deviations that contradict the information contained in the Informed Consent/Accent forms will be considered Major Deviations.

Clinical Study Protocol **Johnson & Johnson Vision Care, Inc.**

Minor deviations have no substantive effect on patient safety or technical integrity of the study. They are often logistical in nature.

Protocol waivers are prohibited.

Table 6 lists examples of deviations that will constitute major and minor protocol deviations for this study.

Table 6: Examples of major and minor protocol deviations

Deviation category	Major deviation	Minor deviation
Out-of-window visit	Visit attended 2-4 days out of visit window defined in study procedures if subject did not meet per protocol wear time. Visit attended more than 4 days out of visit window defined in study procedures regardless of wear time compliance.	Visit attended 2 or fewer days out of visit window defined in study procedures. Visit attended up to 4 days out of visit window and subject has met wear time compliance.
Unanswered PRO questions	Not applicable.	For questionnaires where data where any PRO questions are unanswered (i.e., left blank).
Insufficient wear of study lenses	Not applicable.	Subject does not wear study lenses for at least 1 hour prior to attending a follow-up visit or subject does not wear study lenses for at least 8 hours on at least 10 days of a study lens wear period.

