14.3. Analysis Populations

The following analysis populations will be defined and used in the analysis and presentation of the data.

Safety Population:

All subjects who are administered any test article excluding subjects who drop out prior to administering any test article. At least one observation should be recorded. Subjects will be analyzed as per treatment received.

Per-Protocol Population:

All subjects who successfully complete all visits and do not substantially deviate from the protocol as determined by the trial cohort review committee prior to database hard lock. Justification for the exclusion of subjects with protocol deviations from the per-protocol population set will be documented in a memo to file. See section 10 for definition and examples of major deviations.

Intent-to-Treat (ITT) Population:

All randomized subjects regardless of actual treatment and subsequent withdrawal from the study or deviation from the protocol. At least one observation should be recorded. Subjects will be analyzed as per randomized treatment.

Clinical Study Protocol

Johnson & Johnson Vision Care, Inc.

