14.5. Primary Analysis

Primary Efficacy Endpoint

Binocular Distance (4m) logMAR Visual Acuity (VA)

Non-inferiority of the EMO-118 compared to the MiSight lens with respect to the primary endpoint of distance binocular HLHC logMAR visual acuity will be assessed on the Per-protocol population (PP).

The distance binocular logMAR VA under HLHC will be analyzed using a linear mixed model at the follow-up evaluation. The model will include lens type, lens sequence, period, and first-order carryover as fixed effects and interaction between lens type and period will be evaluated. Other subject characteristics such as age, gender and race will be included as fixed covariates when appropriate. Site will be included in the model as a random effect (G-side). The covariance of residuals between measurements from different periods within the same subject (R-side) will be modeled using Unstructured (UN) covariance structure. If the model does not converge, the compound Symmetry (CS) covariance structure will be considered. The Kenward and Roger method will be used for the denominator degree of freedom.²⁸

Hypothesis Testing

The null and alternative hypotheses for testing non-inferiority of the EMO-118 lens relative to the MiSight lens with respect to logMAR visual acuity are as follows:

$$H_0: \mu_{EMO118} - \mu_{MiSight} \geq 0.05$$
$$H_A: \mu_{EMO118} - \mu_{MiSight} < 0.05$$

Where, μ_{EMO118} represents the mean logMAR VA score for the EMO-118 lens and $\mu_{MiSight}$ represents the mean logMAR VA score for the MiSight lens. Non-inferiority will be declared if the upper bound of the 2-sided 95% confidence interval (CI) of the mean difference (EMO-118 – MiSight) is less than 0.05.

Primary Safety Endpoint

Primary safety endpoint will be evaluated by tabulations of contact lens related (i.e., related and possibly related) serious and significant ocular adverse events and will be summarized by treatment across all visits. The tables will present the number and percentage of eyes and subjects by diagnosis and sorted by decreasing frequency based on the total number of reports.

Additionally, all ocular and non-ocular adverse events will be summarized by seriousness (i.e., ocular AEs by serious, significant and all other ocular AEs, and non-ocular AEs by serious and non-serious), relatedness, severity and diagnosis. A listing of all adverse events including all

Clinical Study Protocol

Johnson & Johnson Vision Care, Inc.

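### Section 8.2 requires withdrawal for refusing any procedure, exploratory charts and questionnaires included, so a child withdrawn for this at Visit 2, 3 or 4 leaves the primary analysis

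*Combined protocol and SAP*

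**What the plan says.** Section 8.2 is mandatory in form: withdrawal follows from any listed reason. One reason is "Subject not compliant to protocol (e.g., refusing any protocol specified procedure". Investigator judgment has its own bullet, tied to subject safety. Section 10 adds "Protocol waivers are prohibited".

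The consequences of withdrawal are set out in several places:

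- On leaving, the site must "Complete the current visit (scheduled or unscheduled" and then do the Final Evaluation (8.2).
- There is no replacement: "Additional subjects will not be enrolled if a subject discontinues from the study prematurely" (8.2).
- A completer must "have not withdrawn/discontinued from the study for any reason described in section 8.2" (8.1).
- The per-protocol population is "All subjects who successfully complete all visits and do not substantially deviate from the protocol as determined by the trial cohort review committee" (14.3).
- The primary non-inferiority comparison "will be assessed on the Per-protocol population (PP" (14.5). Intent-to-treat analyses are optional (14.7), and the main analysis does not impute missing values (14.9).

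Table 6 in section 10 has a row for questionnaires in which "any PRO questions are unanswered (i.e., left blank". That is a minor deviation, and the major column is marked not applicable.

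**The concern.** The refusal rule treats all procedures alike. Declining the slit lamp and declining a near low-contrast chart have the same result, although the second feeds only a descriptive exploratory summary. The subjects may be as young as 7, and each follow-up asks for a long series of acuity readings of which one is primary. The near charts come after the distance step, so a child can give a valid primary reading, decline a near chart, and still trigger withdrawal. This holds even at Visit 2, where the lens under test is the run-in lens (4.1).

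What is at stake is avoidable loss. A child who would have gone on giving primary readings is removed to protect the completeness of data that carry no hypothesis test.

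**Working it through.** **1. The plan's own figure.** Section 14.2 powers the primary test as a paired t-test with SD 0.084 for both lenses, margin 0.05, and two-sided 5% (2.5% in the relevant tail). With SD of the difference = 0.084 × √(2(1 − ρ)) and noncentrality = (0.05 − Δ) / (SD of the difference / √n), n = 50 gives:

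- ρ = 0.3: SD of the difference 0.0994, standard error 0.01406. Noncentrality is 3.56 for Δ = 0 (power 93.7%) and 2.85 for Δ = 0.01 (79.7%).
- ρ = 0.5: SD of the difference 0.0840, standard error 0.01188. Noncentrality is 4.21 for Δ = 0 (98.5%) and 3.37 for Δ = 0.01 (91.0%).

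These match Table 8, as do the other eight cells. The sample size calculation is not in dispute.

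**2. How far the rule reaches.** The distance step (2.6 and 5.7) covers three conditions, each binocular and monocular: 3 × 2 = 6 readings, matching the six charts listed. The near step (2.7 and 5.8) adds 2. Of these 8, section 2.2 makes one primary (binocular high-luminance high-contrast at 4 m) and the other 7 exploratory. Visits 3 and 4 reuse the Visit 2 steps.

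**3. What one withdrawal loses.** Study-lens readings fall at Visits 3, 4 and 5. Because the current visit is completed, that visit's reading is taken even when the refusal comes first. The primary contrast needs both EMO-118 and MiSight, so I enumerated the six sequences of section 5.1:

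| Withdrawn at | Study-lens readings taken | Never taken | Sequences with both contrast lenses read | Readings in the per-protocol test |
|---|---|---|---|---|
| Visit 2 | 0 | 3 | 0 of 6 | 0 |
| Visit 3 | 1 | 2 | 0 of 6 | 0 |
| Visit 4 | 2 | 1 | 2 of 6 | 0 |

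The 2 of 6 at Visit 4 are the sequences with EMO-114 last. There the forgone reading lies outside the primary contrast, and both relevant readings exist, yet the all-visits rule still excludes the child.

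**4. Headroom.** 75 − 50 = 25 losses, and 25/75 = 33.3%. For scale only: if completers fell from 50 to 49, power in the four scenarios (Δ = 0 with ρ = 0.3 and 0.5, then Δ = 0.01 with ρ = 0.3 and 0.5) would be 93.2%, 98.3%, 78.8% and 90.4%, a cost of roughly 0.2 to 0.9 points. Nothing in the documents says refusals would bring completers below 50.

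**5. Section 8.2 against Table 6.** Completing the questionnaires is a scheduled procedure (2.4, 2.26, 5.5), so refusing one falls under 8.2 and means withdrawal. Table 6 grades blank answers as minor only, a class that section 10 describes as having no substantive effect. An item left blank by oversight engages Table 6 alone. The two pull apart only where the blank comes from refusal.

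**The case against.** The best reply is that 8.2 is not meant for every single lapse. It also lists non-compliance with the wear schedule, yet Table 6 grades insufficient wear as minor only; if 8.2 applied to each lapse, that row would have little purpose. Section 10 speaks of tracking deviations and correcting them as appropriate, and refusal is only an example of a non-compliant subject. This stands as evidence that a lenient reading may be intended. It does not settle the matter, because the example given is refusal of any one procedure, nothing authorises a site to overlook it, and waivers are barred.

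It can also be said that a child who refuses one letter chart may soon refuse the primary one. The documents give no evidence either way, so the later readings are obtainable only if the child keeps cooperating.

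A reader might infer that 8.2 and Table 6 contradict each other outright. They do not: Table 6 sets the class of a deviation and 8.2 decides retention, and a subject can be both graded and withdrawn. The awkwardness is confined to refused questionnaires or items.

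**Conclusion.** The point holds as a matter of wording. Applied as written, 8.2 removes a child from the primary analysis for declining an exploratory chart or questionnaire at Visit 2, 3 or 4. Per affected child, 3, 2 or 1 study-lens readings are never taken, and none of those already taken enters the per-protocol test. This assumes that sites follow the text literally and that the child would otherwise have continued.

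Three stronger conclusions are tempting and unsupported:

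- **Lost power or bias.** No refusal rate is given, the allowance covers 25 losses of all kinds, and nothing indicates which lens a refusal would favour.
- **The same loss at Visit 5.** All three readings exist by then and the visit is still completed. Section 8.1 would deny completer status, but 14.3 does not refer to 8.1, so inclusion turns on how the cohort review committee reads successful completion of all visits.
- **Every forgone reading being primary evidence.** EMO-114 is outside the primary contrast.

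Severity is low; the change is worth making because it is cheap.

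**What to change.** Keep the 8.2 bullet and add one exception: *Refusal of an exploratory acuity test in steps 2.6/2.7 or 5.7/5.8 (any reading other than binocular HLHC at 4 m), or of a written PRO questionnaire (post-fit, follow-up, PROMIS PGH7), is not by itself a reason for withdrawal; record it as missing and as a protocol deviation, and the subject continues.*

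Everything else stays under the existing rule: the verbal ocular-symptoms questionnaire, slit lamp, spherocylindrical logMAR acuity, over-refraction, fit assessment, power modification and all continuance criteria. A child who skips the post-fit questionnaire must still say whether comfort and vision are acceptable (criterion 2 of step 2.28).

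Add a Table 6 row for a refused exploratory acuity test: minor when isolated, with repeated refusal across visits referred to cohort review. That keeps a route to exclude a child who refuses most of the testing.

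The cost is one sentence, one table row and some incomplete exploratory acuity and questionnaire data. Under 14.7 the exempted acuity readings are only summarised descriptively, and the questionnaires are summarised and used for psychometric work. Section 14.9 already has missing values counted in the tables. Lens power selection and safety examinations are untouched.

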9. PRE-STUDY AND CONCOMITANT INTERVENTION/MEDICATION

Concomitant medications will be documented during screening and updated during the study. Disallowed medications for this study include:

1. Any medication or therapy that would normally contraindicate contact lens wear or have ocular side effects that would affect vision assessment.
2. Topical atropine or other medications that may temporarily impact pupil size

Concomitant therapies that are disallowed include:

1. Orthokeratology
2. Vision therapy/orthoptics/patching

Clinical Study Protocol

Johnson & Johnson Vision Care, Inc.

3. Any therapies that the investigator feels would be contraindicated in contact lens wear or would affect vision assessment

